- d. **The hours from block placement until hospital discharge will be calculated.**

b. What is the probable length of time required for the entire protocol (i.e., recruitment through data analysis to study closure)? **One year.**

c. What is the total amount of time each participant will be involved? **Each participant will be involved in the study for approximately 48 hours. Each procedure time period is listed below.**

d. If different phases are involved, what is the duration of each phase in which the participants will be involved? If no phases are involved, enter "None." **None**

e. List the procedures, the length of time the procedure takes, the total # of times the procedure is performed, and indicate whether each is performed solely for research or would already be performed for treatment or diagnostic purposes (routine care) for the population.

-Insert additional table rows as needed.

-If procedure is sometimes research and sometimes routine care, include on separate lines with number of times as each.

Procedure	Length of Time Required of Participants	Frequency of Repetition	Research (Res) – OR- Routine Care
Pre-surgical Evaluation on the day of surgery	30 minutes	once	 Res  Routine
Randomization on day of surgery	5 minutes	Once	 Res  Routine
Placement of block	Approximately 30 min.	Once	 Res  Routine
Post Anesthesia Care Unit (PACU) assessment	10 minutes	Once	 Res  Routine
First postoperative assessment survey (approximately 24 hours after surgery)	10 minutes	Once	 Res  Routine
Second postoperative assessment survey (approximately 48 hours after surgery)	10 minutes	Once	 Res  Routine

- f. Will an interview script or questionnaire be used? Yes No
If Yes, attach a copy.
- g. Will participants incur any costs as a result of their participation? Yes No
If Yes, describe the reason for and amount of each foreseeable cost. _____
- h. Will participants be compensated? Yes No
If Yes, complete i-v.
i. Type: (e.g., cash, check, gift card, merchandise): _____

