General Data Analysis Plan: All demographic and clinical variables with continuous measures will be expressed as means and standard deviations; categorical factors will be expressed as proportions. For non-normal data, the medians and inter quartile ranges will be displayed. The distribution of the continuous factors will be examined using the Kolmogorov-Smirnov test. For data that are normally distributed, the one-way ANOVA and Student's t-test will be used to compare groups of data. For data that are not normally distributed, the Kruskal-Wallis and Mann-Whitney tests will be used for comparisons. Chi-square and Fisher's exact tests will be used to analyze categorical data. For all comparisons, a value of $p < 0.05$ will be considered statistically significant.

Primary Outcome Analysis: Statistical analyses will be performed using SAS for Windows, version 9.2. Student's t-test will be used to compare post-operative pain scores for investigational and control subjects. Linear regression will be also be used to test the relationship between pain scores and regional anesthetic technique, while controlling for relevant clinical and demographic variables. Distance of first ambulation will be analyzed using Cox proportional-hazards model. Student's t-test will be used to compare patient and surgeon satisfaction.

Statistical Power and Sample Size Estimates : Sample size (50 each group) was determined using a Cohen's d table assuming a mean pain VAS score of 8 (SD = 3) on a scale of 0-10 for control subjects. A difference of VAS score of 3 between two study groups will be clinically relevant. A sample of 100 participants (50 patients per group) will have approximately 95% power to detect a reduction in pain score difference of 3 with significance level alpha of 0.05. We will perform an interim analysis after 50 patients have completed the study (25 patients in each group).

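### The sample-size figures do not reconcile: a difference of 3, SD 3 and 50 per group give about 99.9% power, and the stated 95% would need about 27 per group.

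*Combined protocol and SAP*

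**What the plan says.** The sizing is in Statistical Considerations, under Statistical Power and Sample Size Estimates. It says that 50 per group was read from a Cohen's d table, "assuming a mean pain VAS score of 8 (SD = 3) on a scale of 0-10 for control subjects". The target is given next: "A difference of VAS score of 3 between two study groups will be clinically relevant". The resulting claim is "A sample of 100 participants (50 patients per group) will have approximately 95% power to detect a reduction in pain score difference of 3". The alpha attached to that claim is 0.05.

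The matching test is under Primary Outcome Analysis, where Student's "t-test will be used to compare post-operative pain scores for investigational and control subjects". The General Data Analysis Plan sets a single threshold: "For all comparisons, a value of $p < 0.05$ will be considered statistically significant". Item 16.a gives enrolment as 100, and item 16.e gives 1:1 randomisation. Item 17.c says: "Each participant will be involved in the study for approximately 48 hours".

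The plan does not state whether the test is one- or two-sided, what SD is expected in the block group, or any allowance for dropout, multiple endpoints or the interim analysis.

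**The concern.** The difference, the SD, the group size, the alpha, the test and the power all appear within a few sentences. Any one of them is fixed by the other five. A difference of 3 against an SD of 3 is a standardised effect of 1.0, which is large, and 50 per group is far more than a t-test needs to detect it with 95% power. The printed power therefore looked too low for the printed N, or the N too high for the printed power.

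The paragraph is the only rationale for enrolling 100 patients. If the figures conflict, a reader or ethics board cannot tell why 100 was chosen. An input that the plan does not show may lie behind it, such as a larger SD, a smaller difference, or a dropout or alpha allowance.

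**Working it through.** **Inputs**

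| Input | Value | Source |
|---|---|---|
| Difference in mean pain score | 3 | Statistical Power and Sample Size Estimates |
| SD | 3 (controls); assumed common to both groups | same paragraph |
| n per group | 50 | same paragraph |
| Alpha | 0.05; two-sided assumed | same paragraph; General Data Analysis Plan |
| Allocation | 1:1 | item 16.e |
| Test | two-sample Student's t | Primary Outcome Analysis |
| Stated power | about 95% | Statistical Power and Sample Size Estimates |

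**1. Try to reproduce the stated 95%.**

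d = 3/3 = 1.0. Degrees of freedom = 2 × 50 − 2 = 98. Noncentrality = d × √(n/2) = 1.0 × √25 = 5.0. The two-sided critical value is t(0.975, 98) = 1.984.

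Power = P(|T| > 1.984), where T is noncentral t with 98 df and noncentrality 5.0. The result is **99.86%**. The normal approximation gives 99.88%, and a one-sided test gives 99.96%. A simulation of 100,000 trials (normal data, means 8 and 5, SD 3, 50 per group) gave 99.85%. The stated figure is not reproduced.

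**2. Sample size for 95% power at d = 1.0 (exact t, two-sided).**

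| n per group | Power |
|---|---|
| 25 | 93.4% |
| 26 | 94.2% |
| 27 | 95.0% |
| 50 | 99.86% |

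So 27 per group, 54 in total (26 per group by the normal approximation; 23 per group if one-sided).

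**3. What would bring 50 per group down to 95%, changing one input at a time?**

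- *Loss of patients.* 20% loss (n = 40) leaves 99.3%, and 40% loss (n = 30) leaves 96.8%. Reaching 95.0% takes a fall to 27 analysed, a loss of (50 − 27)/50 = 46%.
- *Stricter alpha.* 0.025 gives 99.6%, 0.0125 gives 99.2% and 0.01 gives 99.0%. Power reaches 95.0% at alpha of about 0.0013.
- *Smaller difference.* Solving for d at n = 50 and 95% power gives d = 0.728, so a difference of 0.728 × 3 = 2.18 points.
- *Larger SD.* 3/0.728 = 4.12 pooled. Power for 3 points is 98.9% at SD 3.5 and 96.0% at SD 4.0.

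**4. Are those SDs possible on a 0–10 scale?**

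The largest SD for a variable on 0–10 with mean m is √(m(10 − m)). For controls with mean 8 that is √(8 × 2) = 4.0, so a common SD of 4.12 cannot occur. If the control SD stays at 3, a pooled SD of 4.12 requires a block-group SD of √(2 × 4.12² − 9) ≈ 5.0. With a block mean of 8 − 3 = 5, the maximum is √(5 × 5) = 5.0, reached only if every score is 0 or 10. A block-group SD of 4 still gives 98.7%.

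**5. A rank test instead.**

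The General Data Analysis Plan allows Mann-Whitney for non-normal data. At the worst-case relative efficiency of 0.864 the effective n is about 43 per group, and power is 99.6%.

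**6. What 50 per group can detect with SD 3.**

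| Power | d | Difference (d × 3) |
|---|---|---|
| 95% | 0.728 | 2.18 points |
| 90% | 0.655 | 1.96 points |
| 80% | 0.566 | 1.70 points |

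**The case against.** The best technical objection is that the SD of 3 is given for controls only, so the printed figures conflict only under a common SD. Strictly that is right. A block-group SD near 5 would restore 95% with every printed number intact. But it would need every block patient to score 0 or 10, so it is not a credible reading.

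A second objection is that the 100 may include allowances the authors did not write down. No ordinary single allowance is enough. A combination could be: 20% loss together with alpha divided by 8 gives 94.8%. The plan states neither, follows patients for only about two days, and applies 0.05 to every comparison. Item 14.b also lists several primary endpoints, and 100 patients may have been wanted for those, but no calculation for them is given.

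A third possibility is that a total of 50 was misread as 50 per group. At 25 per group, the interim size in the same paragraph, power is 93.4%. That is conjecture.

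The fair point on weight is that the error is conservative and that correcting it changes neither enrolment nor the pain comparison. That limits its importance. It does not make the stated power right.

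**Conclusion.** The concern holds. On the stated inputs, power for a 3-point difference is 99.86%, against a stated figure of about 95%. That is 4.9 percentage points higher, or a type II error of 0.14% rather than 5%. The stated power would be met with 54 patients, not 100.

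This rests on a common SD of 3 and two-sided testing. One-sided testing widens the gap, and no plausible block-group SD closes it. The documents show that the figures conflict but not which one is the slip. The trial is not underpowered for its 3-point target. The fault is that the enrolment figure cannot be derived from its only justification, and that the plan does not show the smaller differences the design can detect. It should be fixed, but it does not threaten the trial.

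**What to change.** Keep 50 per group and replace the power sentence with, for example: *Assuming a common SD of 3 and two-sided alpha of 0.05, 50 patients per group give more than 99% power for a 3-point difference in mean pain score, 95% for 2.2 points, 90% for 2.0 points and 80% for 1.7 points.*

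If a different SD, difference, dropout allowance or alpha allowance lay behind the 100, state it and recompute the power from it. A restated SD must be feasible on a 0–10 scale: with a control mean of 8, the control SD cannot exceed 4.0.

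The cost is one sentence in the statistical section. Enrolment, test and alpha do not change.

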a. Describe precautions that will be taken to avoid risks and the means for monitoring to detect risks.

We will use the standard precautions for placement of regional blocks which include sterile technique and ultrasound-guided placement. Patients will be monitored during regional block placement with pulse oximetry, EKG, non-invasive blood pressure and capnograph monitors. Regional block will be performed under routine sterile conditions.

A data and safety monitoring plan will be implemented by Drs. [name] and [name] to ensure that there are no changes in the risk/benefit ratio during the course of the study and that confidentiality of research data is maintained. This will be achieved by close following of study participants to screen for adverse events and interim results analysis during data collection phase. Investigators and study personnel will meet either electronically or in person, monthly (more often if needed) during active participant enrollment to discuss the study (e.g., study goals and modifications of those goals; subject recruitment and completion; progress in data coding and analysis; documentation, identification of adverse events or research subject complaints; violations of confidentiality) and address any issues or concerns at that time. A DSMB committee will review outcomes and any adverse events as they occur or every six months (if no adverse or reportable events). The DSMB consists of [name], [name], [name], [name].

If the protocol involves drugs or devices skip Items 20.b. and 20.c. and go to Item 21. Instead include this information in the [Drug Review Sheet](#) or [Device Review Sheet](#), as applicable.

b. If hazards occur to an individual participant, describe (i) the criteria that will be used to decide whether that participant should be removed from the protocol; (ii) the procedure for removing such participants when necessary to protect their rights and welfare; and (iii) any special procedures, precautions, or follow-up that will be used to ensure the safety of other currently enrolled participants. **If the patient meets the inclusion criteria, the block will be administered. Any negative event will be evaluated and treated as per standard of care. Each patient will have immediate follow-up evaluation performed by the PI or co-investigators to look for safety concerns.**

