c. If hazards occur that might make the risks of participation outweigh the benefits for all participants, describe (i) the criteria that will be used to stop or end the entire protocol and (ii) any special procedures, precautions, or follow-up that will be used to ensure the safety of currently enrolled participants.

Quadratus lumborum blocks are described for perioperative analgesia for abdominal procedures and hip arthroplasty. We do not anticipate additional risks for the patients who choose to participate in the study, as compared to other patients who undergo truncal blocks.

A data and safety monitoring plan will be implemented by Drs. [name] and [name] to ensure that there are no changes in the risk/benefit ratio during the course of the study and that confidentiality of research data is maintained. This will be achieved by close following of study participants to screen for adverse events and interim results analysis during data collection phase. Investigators and study personnel as well as the DSMB (consisting of clinicians and scientists: [name], [name], [name], [name]) will meet either electronically or in person, to evaluate any adverse or reportable event every six months during active participant enrollment.

21. Informed Consent

- a. Do you plan to obtain informed consent for this protocol? Yes No
If Yes, complete the items below.
If No, complete and include the [Waiver of Informed Consent](#) or [Waiver of Authorization and Informed Consent](#), as applicable.
- b. Do you plan to document informed consent (obtain signatures) for this protocol? Yes No
If Yes, complete the items below.
If No, complete the items below and include the [Waiver of Informed Consent Documentation](#).
- c. How will consent be obtained? **The interviewing investigator will confirm eligibility and absence of any exclusionary criteria. Details of the study (including risks) will be explained to prospective participant to their satisfaction and consent forms will then be signed.**

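### The 50-patient interim analysis has no end point, decision or boundary; if pain is tested at p < 0.05 at both looks and either result can count, type I error is about 8.3%, not 5%

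*Combined protocol and SAP*

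**What the plan says.** Three parts of the combined protocol and SAP bear on this.

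- **Statistical Considerations, Statistical Power and Sample Size Estimates.** The paragraph justifies 50 patients per group on pain scores, claims "approximately 95% power to detect a reduction in pain score difference of 3 with significance level alpha of 0.05", and closes with "We will perform an interim analysis after 50 patients have completed the study (25 patients in each group"). No end point, test, decision, boundary or adjusted final threshold is given.
- **Statistical Considerations, General Data Analysis Plan.** The one significance rule is "For all comparisons, a value of $p < 0.05$ will be considered statistically significant".
- **Items 20.a and 20.c.** The monitoring plan includes "interim results analysis during data collection phase", with the aim "to ensure that there are no changes in the risk/benefit ratio during the course of the study". Two named doctors implement it. Item 20.a has a monthly investigator meeting whose agenda includes "progress in data coding and analysis", and also says "A DSMB committee will review outcomes and any adverse events as they occur or every six months". Item 20.c has investigators and the DSMB meeting to evaluate adverse or reportable events. Neither item mentions the 50-patient look.

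The form also directs: "If the protocol involves drugs or devices skip Items 20.b. and 20.c. and go to Item 21". Hazard and stopping content for drug studies belongs in a Drug Review Sheet, which is not among the documents. A safety stopping rule may be there, so the gap described here is only the missing efficacy rule.

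**The concern.** The interim sentence sits in the paragraph that powers the pain comparison, directly after the statement of alpha, and the 0.05 threshold makes no exception for it. Someone following the plan could test pain at 0.05 at 50 patients, test it again at 0.05 at 100, and report either result as positive. The error rate for that comparison would then exceed the 5% on which the power statement rests.

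Timing matters as much as size. If the interim gives p < 0.05 and no rule exists, the team must decide what the result means after seeing it. A boundary chosen at that stage does not protect the error rate.

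**Working it through.** **Inputs.** One look at 25 per group out of 50 per group, so the information fraction is 0.5; difference 3 points, SD 3, so d = 3/3 = 1; alpha 0.05 (all from Statistical Power and Sample Size Estimates). The threshold is 0.05 (General Data Analysis Plan) and the test is Student's t (Primary Outcome Analysis). The plan does not state sidedness; two-sided is assumed.

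**1. The plan's own power figure.** The noncentrality is d/√(2/n).

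- n = 50: 1/√(2/50) = 5.00, power 99.86%.
- n = 25: 1/√(2/25) = 3.54, power 93.4%.

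The stated 95% at 50 per group therefore does not reproduce from the stated inputs. That is a separate matter, but it leaves the intended effect uncertain. The effect that does give 95% at 50 per group is d = 0.728, or 0.728 × 3 = 2.18 points. It is solved backwards and is not in the documents; it serves here as a less favourable case.

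**2. Type I error with two looks at 0.05.** The interim and final z statistics have correlation √(25/50) = 0.707. Under no difference:

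1 − P(|Z₁| < 1.96 and |Z₂| < 1.96) = 0.0831.

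Simulated t-tests at 25 and then 50 per group agree: 8.30% in 1,000,000 trials and 8.24% in a separate 400,000. With one-sided 0.05 at each look the figure is 8.0%. If only the final test counts, the simulated error is 4.93% to 4.97%, that is, the nominal 5%.

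**3. Chance of p < 0.05 at the interim (noncentral t, 25 per group).** 93.4% at d = 1; 71.3% at d = 0.728.

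**4. Boundaries that keep 5% with one look at half the information.**

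- O'Brien-Fleming, constant 1.9774: interim |Z| > 1.9774 × √2 = 2.797, p < 0.0052; final |Z| > 1.9774, p < 0.0480.
- Pocock, constant 2.1783: p < 0.0294 at both looks.

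**5. Error and overall power of each rule.** Figures are from the 400,000-trial simulations, except the value marked *, which is noncentral t.

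| Rule | Type I error | Power, d = 1 | Power, d = 0.728 |
|---|---|---|---|
| Final test only, 0.05 | 4.93% | 99.86%* | 94.99% |
| Either look at 0.05 | 8.24% | – | – |
| O'Brien-Fleming | 4.97% | 99.85% | 94.86% |
| Pocock | 4.94% | 99.75% | 92.97% |
| Futility stop at interim p > 0.5 (illustration), final 0.05 | 4.48% | 99.68% | 93.47% |

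Considering the final test alone, moving its threshold from 0.05 to 0.048 takes power from 99.86% to 99.85% at d = 1, and from 95.0% to 94.8% at d = 0.728.

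**The case against.** The strongest reply is that the 8.3% needs two things no sentence in the plan states: that pain is tested at 50 patients, and that an interim p < 0.05 may count as success. Items 20.a and 20.c give interim review a risk/benefit purpose and a DSMB. If the 50-patient look is that review, no alpha is spent and one clarifying sentence is enough. This is a reasonable reading, and it is why the 8.3% is conditional. But no text links the two, and the 0.05 rule is not limited to the final analysis.

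Other points stand in part:

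- The evidence on who sees results is thin. The joint meeting in item 20.c is for adverse or reportable events, and the monthly agenda item in 20.a concerns progress, not results by group. What remains is that access to between-group interim results is not stated.
- A significant interim result under the assumed effect would be a true positive. The 93% shows that the question will arise, not that false positives are common.
- The d = 0.728 case is one reading of a power figure that does not match its inputs. The conclusion does not depend on it.
- The plan lists several primary end points and pain times, so this look is only one source of inflated error.

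**Conclusion.** The concern holds. The plan schedules an interim analysis without saying what is tested, what may follow, or at what threshold, and its general rule permits 0.05 at both looks. For a single pain comparison tested two-sided at 0.05 at 25 and 50 per group, with either result able to count, type I error is 8.3%. If only the final test can support the claim it is 5%, even if pain is looked at in the interim. The size applies to one comparison only: settling this look does not by itself hold the whole trial to 5%. It should be fixed, and before the look takes place.

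**What to change.** Add one of the following to the sample-size paragraph before the interim data are examined.

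- **(a) The look may support an efficacy claim.** Name one pain comparison at one time point and a boundary that keeps 5% overall for it, for example O'Brien-Fleming: p < 0.0052 at the interim and p < 0.048 at the end. The time point has to be chosen, because item 14.b lists three pain assessments and item 15 lists four.
- **(b) It may not.** State that the look is for safety or futility, or otherwise cannot support a claim of efficacy. The final test stays at 0.05, and the DSMB can still review outcomes for risk/benefit as item 20.a provides.

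In either case, state who sees between-group interim results, preferably the existing DSMB. Reconcile this with the roles in items 20.a and 20.c, and cross-refer to the Drug Review Sheet if it holds stopping criteria.

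**Cost.** About three sentences plus matching edits to items 20.a and 20.c, and no extra patients; option (a) also requires the decision on a pain time point. O'Brien-Fleming costs at most about 0.2 percentage points of final-test power. Pocock costs about 2 points at d = 0.728 (94.99% to 92.97%), so it is not the suggested example. Option (b) without a futility stop costs no alpha and no power. A futility stop needs no alpha adjustment but loses some power, about 1.5 points at d = 0.728 in the illustration above.
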